Early hemorrhoids are frequently treated with a fiber diet and with lifestyle modifications such as increased exercise and the avoidance of obesity and sedentary occupation which appear to be significant risk factors for the disease. Also, control of diarrhea appears to be a useful option in the prevention of the development of hemorrhoids. However, in more advanced cases acute hemorrhoidal attacks are present with bleeding, inflammation and often thrombosis of the hemorrhoidal veins. Conservative therapy consists of local treatment. Several types of drugs have been used for this purpose. These include local anesthetics, chiefly pramoxine. This is a rapidly acting, local anesthetic which is applied topically as needed up to five times a day. It provides local relief particularly of itching through its anesthetic action. Local application of phenylephrine is also used in the treatment of hemorrhoids to reduce blood flow through the hemorrhoids by utilizing the drug's vasoconstricting action. This produces temporary relief of burning and itching. 5-amino salicylic acid (Mesalamine) is also used off-label as a local antiinflammatory agent to treat hemorrhoids. It appears to reduce the pain and bleeding of hemorrhoids during acute attacks. Hydrocortisone in various types of vehicles is also a prominent modality of treatment for hemorrhoids as well as other anorectal conditions. Foams, suppositories and locally applied creams have been used as vehicles for the application of hydrocortisone, although none are FDA-approved products for the treatment of hemorrhoids. Hydrocortisone's potent anti-inflammatory action is thought to reduce the inflammation associated with the hemorrhoids and thus improve bleeding, itching and other symptoms of hemorrhoids. Products using these ingredients have a long history of use in the United States and are commonly relied upon for the non-surgical, conservative treatment of hemorrhoids.

26Apr2019 Protocol: **HDCS 1701** Page 6 of 67 Version 4.0

3. OBJECTIVE:

- a. To determine the effectiveness of Nivagen's Hydrocortisone Acetate Suppositories 25 mg for the relief of symptoms associated with internal hemorrhoids.
- b. To determine the safety and tolerability of Nivagen's Hydrocortisone Acetate Suppositories 25 mg.
- 4. PHASE: 2

5. STUDY DESIGN:

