This study will be a randomized, double-blind, placebo-controlled, multicenter, parallel group pilot study of 25 mg hydrocortisone suppositories administered twice daily compared to a vehicle placebo in subjects with symptomatic internal hemorrhoids. Approximately 100 subjects will be randomized in a 1:1 ratio (Test product: placebo).

The study will consist of 3 periods:

- a. Screening Period (2 weeks/Days -14 to -1)
- b. Treatment Period (2 weeks/ Days 1-14)
- c. Follow-up Period (2 weeks/ Days 15-29)

Subjects will use daily paper diaries to record the time and date of each medication application, concomitant medication and adverse events (AEs). The subjects will use electronic diaries to complete the Internal Hemorrhoids Sign and Symptom Assessment (IHSSA) daily for the duration of the study and the Patient Global Impression of Severity (PGIS) and Change (PGIC) at visits.

6. STUDY POPULATION:

Male and female subjects, at least 18 years of age, with a diagnosis of symptomatic internal hemorrhoids will be selected to participate in the study.

7. PRODUCT DESCRIPTION:

Test Product: Hydrocortisone Acetate Suppository, 25 mg (Nivagen Pharmaceuticals Inc.) Placebo: Vehicle Suppository (Nivagen Pharmaceuticals Inc.)

8. GROUPS:

Two Groups (1:1) Total Subjects: Approximately 100 (50:50)

9. STUDY SCHEDULE:

Visit 1 (Days -14±2; Initiation of Screening)

Visit 2 (Day 1; Start of Treatment)

Visit 3 (Day 8±1, Interim)

Visit 4 (Day 15±2, End of Treatment)

Visit 5 (Day 29±3, Follow-Up/End of Study; UV/ED)

26Apr2019 Protocol: **HDCS 1701** Page 7 of 67 Version 4.0

10. STUDY OUTLINE:

Visit Title	Initiation of Screening	Start of Treatment	Interim	End of Treatment	Follow-up/End of Study UV/ED ⁸
Visit Number	Visit 1	Visit 2	Visit 3	Visit 4	Visit 5
Study Day	Day -14±2	Day 1	Day 8±1	Day 15±2	Day 29±3
Informed Consent	X				,
Medical History	X				
Demographics	X				
Concomitant Medication	37	37	37	37	37
Review	X	X	X	X	X
Physical Exam including Vital Signs	X				
Clinical Laboratory Tests	X ¹		X^2	X^3	
Urine Pregnancy Test ⁴	X	X	X	X	X
Urine Drug Screen	X				
Breath Alcohol Test	X				
Inclusion/Exclusion Criteria	X	X			
Adverse Events Assessment		X	X	X	X
Anoscopy		X		X	
Assessment of Disease Grade/ Diagnosis		X			
Randomization		X			
Cognitive Interview ⁵	X				
Exit Interview ⁶				X	
PROMIS Global Health		37			
Questionnaire		X		X	
IHSSA daily diary ⁷ (ePRO)	X	X	X	X	X
Patient Global Impression of Severity (PGIS) (ePRO)		X		X	

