Note that the medication from the suppository may stain fabric. Subjects may experience irritation such as burning, itching, dryness, skin/hair follicle irritation, or changes in skin color around the rectal area. Subjects are to report to the study staff any reactions that make continued application of the study medication difficult. The PI may recommend that the study medication be used less frequently on the irritated areas until the irritation goes away. If subject sees a doctor for any medical problems, they are to be advised to inform the study staff at their next visit. Subject is to record any illness or unwell feelings such as headaches, cold, cramps, etc., on the last page of their diary. Subjects are to record any change in medications since the previous visit (other than study medication) on the last page of the diary. All unused study medication must be returned to the study site at the end of treatment.

15. LABORATORY STUDIES:

comprehensive blood count (CBC), metabolic panel (CMP), blood HIV/Hepatitis B/Hepatitis C testing, urinalysis, urine pregnancy, urine drug screen, breath alcohol tests.

Protocol: HDCS 1701 Page 11 of 67 26Apr2019

16. DIAGNOSTIC TESTS:

Anoscopy - Classification of Internal Hemorrhoids (Banov et al. 1985).

Video of the procedure will be recorded and sent to the CRO for central reading.

Grade	Description
1	Hemorrhoids are visualized on anoscopy and may bulge into the lumen but do not prolapse below the dentate line
II	Hemorrhoids prolapse out of the anal canal with defecation or with straining but reduce spontaneously
III	Hemorrhoids prolapse out of the anal canal with defecation or straining, and require manual reduction
IV	Hemorrhoids are irreducible and may strangulate

17. RETENTION SAMPLES:

Retention samples will be randomly selected at the study sites from the clinical drug supplies received prior to dispensing to subjects and sent to BRR for long-term storage. Retention samples will not be returned to the sponsor at any time.

18. ADMINISTRATIVE MATTERS:

In addition to recording the time and date of each medication application, the Daily Personal Diaries will be used to record concomitant medication taken and all adverse events experienced. Paper copies of the IHSSA daily electronic diaries will be provided to subjects for use as a backup for missed ePRO questionnaires.

19. STUDY DISCONTINUATION:

Subjects could be discontinued from the study for the following reasons:

- a. Pregnancy.

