The Patient Global Impression of Severity (PGIS) and Patient Global Impression of Change (PGIC) items are designed to capture the patient's overall perspective on sign and symptom severity. The 8-item PGIS asks patients to rate the severity of their hemorrhoid-related signs and symptoms over the past week. The 9-item PGIC asks patients to rate the direction and magnitude of the change in their signs and symptoms since starting the study medication. The PGIS and PGIC are included in the study to help establish the threshold for clinically relevant change on the IHSSA. Although they address signs and symptoms of internal hemorrhoids, the IHSSA is considered the primary measure of these constructs. The PGIS and PGIC items are included in **Appendix 3**.

Based on the results of the pilot study, primary and secondary endpoints will be selected for future studies.

22. SUBJECT SAFETY:

a. Safety assessment will be conducted on all subjects administered at least one suppository. Adverse drug reactions may include burning and local irritation upon application. Systemic absorption of topical corticosteroids has produced reversible suppression of the HPA axis. Adverse medical events experienced by the subjects will be tabulated. The relationship of adverse events, if any, to the study drug will be assessed by the Investigator (see Section 24).

26Apr2019 Protocol: **HDCS 1701** Page 14 of 67

b. Physical Examination

The investigator, sub-investigator or appropriately delegated designee, (Physician's Assistant, Advanced Registered Nurse Practitioner, and Registered Nurse as per local regulations) will perform a brief physical examination, prior to the Subject starting study drug.

The physical examination will include, at a minimum, examination of the Subject's general appearance, skin, HEENT (head, eyes, ears, nose and throat), heart, lungs, musculoskeletal system, neurological system, lymph nodes, abdomen and extremities.

Vital signs, including blood pressure, pulse rate, respiratory rate and oral body temperature will be documented at Visit 1. Vital signs will be measured after the Subject has rested in a seated position for at least 5 minutes.

The Subject's body weight will also be measured while the Subject is lightly clothed (e.g., no coat or shoes). Height will be measured without shoes.

c. Concomitant medications

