- ix. Obtaining additional tests to evaluate liver function, as appropriate (e.g., INR, direct
- Considering gastroenterology or hepatology consultations. X.

f. Pilot study stopping criteria

The pilot study may be stopped if ≥2 patients on drug develop the same CTCAE v4.0 Grade 3 adverse event or if 1 patient develops a CTCAE v4.0 Grade 4 or higher adverse event (Appendix 4).

23. STATISTICAL METHODS:

Endpoints

Anoscopy results at Day 15 will be compared to responses at baseline (Day 1). IHSSA scores from Days 1-15 (treatment period) and 16-29 (follow-up period) will be compared to responses from Days -14 to -1 (baseline period). The 95% confidence intervals for the differences between the change from baseline for the hydrocortisone acetate suppository and that for the placebo will be calculated.

b. Safety

The incidence of all AEs reported during the study will be classified based on Medical Dictionary for Regulatory Activities (MedDRA) version 21.0 terminology (system organ classes and preferred terms) and summarized for each treatment group. Incidence of adverse events will be tabulated by system organ class, preferred term, and severity, and by system organ class, preferred term, and relationship to study drug.

24. ADVERSE EVENTS:

Definitions

- Any untoward events occurring during the study will be documented and summarized upon completion of the study.
- The term Adverse Event (AE) will cover any untoward medical occurrence in a clinical investigation where a volunteer was administered an investigational product, which does not necessarily have to have causal relationship with this treatment. An adverse event can therefore be any unfavorable and unintended sign (including clinically significant abnormal laboratory finding, for example), symptom, or disease temporally associated with use of a medicinal product, whether considered related to the medicinal product. This includes all events both expected and unexpected (the nature or severity of which is not consistent with information in the relevant source document(s)).

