- In the pre-approval clinical experience with a new medicinal product or its new usages, particularly as the therapeutic dose(s) may not be established, an Adverse Drug Reaction (ADR) is defined as follows: all noxious and unintended responses to a medicinal product related to any dose. The phrase "responses to a medicinal product" means that a causal relationship between a medicinal product and an adverse event is at least a reasonable possibility, i.e., the relationship cannot be ruled out. Regarding marketed medicinal products, an adverse drug reaction is defined as a response to a drug which is noxious and

Protocol: HDCS 1701 26Apr2019 Page 16 of 67

- unintended, and which occurs at doses normally used in man for prophylaxis, diagnosis, or therapy of disease or for modification of physiological function.
- iv. A medical event is defined as any unintended sign, symptom, or disease that occurs between the pre-trial evaluation and the first investigational product administration of the clinical study. As no investigational product has been administered yet, those events are not to be considered as adverse events.
- v. Worsening of a sign or symptom of the condition under treatment will normally be measured by efficacy parameters. However, if the outcome fulfills the definition of "serious adverse event", it must be recorded as such (see below).
- b. An adverse event may be:
- i. A new illness.
- ii. Worsening of a concomitant illness.
- iii. An effect of the study medication including comparator; it could be an abnormal laboratory value as well as a significant shift from baseline within normal range which the qualified investigator or medical qualified designate considers to be clinically important.
- iv. A combination of two or more of these factors.
- v. Abnormalities in laboratory tests, in the measurements of vital signs, or in other measurements performed after the drug administration or at the end of the study are to be recorded as adverse events only if they are medically relevant: symptomatic, requiring corrective treatment, leading to study discontinuation and/or fulfilling a seriousness criterion. If asymptomatic, but with a suspected underlying process, the qualified investigator or the qualified medical designate may consider the abnormalities to be medically relevant.

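### Safety is objective b, but no vital signs are scheduled after dosing and the laboratory panels have no planned summary by arm, so the safety conclusion rests on reported adverse events

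*Combined protocol and SAP*

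**What the plan says.** Objective b in Section 3 is "To determine the safety and tolerability of Nivagen's Hydrocortisone Acetate Suppositories 25 mg".

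**Vital signs and examination.** Section 22.b: "Vital signs, including blood pressure, pulse rate, respiratory rate and oral body temperature will be documented at Visit 1". The same section says that site staff "will perform a brief physical examination, prior to the Subject starting study drug". In the Section 10 table the row "Physical Exam including Vital Signs" has a single mark, under Visit 1. Section 28 lists vital signs among the Visit 1 procedures and at no later visit. An early-discontinuation visit follows the Visit 5 list (Sections 19 and 28), which has no vital signs, CMP or CBC.

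**Rule for abnormal measurements.** Section 24.b.v applies to abnormal laboratory results and also to abnormalities found "in the measurements of vital signs, or in other measurements performed after the drug administration or at the end of the study". They become adverse events only if medically relevant. An asymptomatic finding with a suspected underlying process may be counted at the investigator's discretion.

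**Laboratory tests.** CMP is drawn at Visits 1, 3 and 4, and CBC at Visits 1 and 4 (Sections 10 and 28). Section 22.e sets liver-enzyme and bilirubin thresholds for individual subjects.

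**Planned safety analysis.** Section 23.b: "The incidence of all AEs reported during the study will be classified based on Medical Dictionary for Regulatory Activities". It then names tables by system organ class and preferred term, crossed with severity and with relationship to study drug. It describes no summary of laboratory values or vital signs.

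**The concern.** Two parts of the plan do not meet. The adverse-event section expects vital signs to be measured after dosing, and the schedule contains none. If blood pressure or pulse moved in one arm, no scheduled measurement would show it, and nobody could recover the data later.

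The laboratory gap is different: the data will exist, but the analysis section does not use them as data. They reach the results one subject at a time, through a judgement of medical relevance. A modest shift in the mean of one arm need not trigger that judgement in any single subject.

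At stake is how to read a clean safety result. The pilot is meant to inform later studies. A statement that no effect on vital signs or laboratory values was seen would partly reflect what was not measured or not summarised.

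**Working it through.** The plan gives no figure on this point, so there is none to reproduce. The check is mainly a comparison of sections, followed by the precision that the added summaries would have.

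**1. Timing of vital signs.** Visit 1 is 14±2 days before Visit 2 (Section 28), and the first suppository is used at home after Visit 2. The only scheduled vital signs therefore precede dosing by 12 to 16 days. Scheduled post-dose values per subject: 0.

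**2. What Section 24.b.v can act on.**

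| Measurement | Scheduled after dosing? | In Section 23.b as values? |
|---|---|---|
| Vital signs | No | No |
| CMP | Visits 3 and 4 | No |
| CBC | Visit 4 | No |
| Adverse events | Visits 3, 4 and 5 | Yes, as incidence |

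The rule works for the laboratory panels. Only its vital-sign clause lacks scheduled data.

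**3. Volume of laboratory data.** If all 100 subjects complete: 100 × 3 = 300 CMP, of which 100 × 2 = 200 are post-dose; and 100 × 2 = 200 CBC, of which 100 are post-dose. A subject who leaves before Visit 3 may have no scheduled post-dose panel.

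**4. Precision of a summary by arm.** For a difference in mean change with n evaluable subjects per arm:

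half-width of the 95% CI = t(0.975, 2n − 2) × √(2/n) × SD of change

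- n = 50 (everyone evaluable): 1.984 × √(2/50) = 1.984 × 0.200 = 0.397 SD.
- n = 40 (assumed, to show the effect of loss): 1.991 × √(2/40) = 1.991 × 0.2236 = 0.445 SD.

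The documents give no SD. If the SD of change in systolic pressure were 12 to 15 mmHg (assumption), the half-width at n = 50 would be 0.397 × 12 = 4.8 to 0.397 × 15 = 6.0 mmHg.

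**5. What event counts alone can show.** With 50 subjects on active drug, the chance of seeing at least one event with a true rate of 2% is 1 − 0.98^50 = 0.636. Zero events in 50 leaves a one-sided 95% upper bound of 1 − 0.05^(1/50) = 5.8%. Summaries of continuous values add information that event counts at this size do not give.

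**The case against.** The strongest reply is that safety monitoring is not confined to volunteered complaints. Chemistry is drawn during treatment and again, with a blood count, at its end. Adverse events are assessed at each visit from Visit 2 and recorded in diaries. The definitions in Section 24 include clinically significant laboratory findings, and 24.b.iii admits a shift within the normal range that the investigator considers important. Such events are tabulated by arm. Section 22.e has liver thresholds for withdrawal, and the reason for any discontinuation is recorded.

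All of that stands, and it limits the point. A reader might infer that systemic steroid effects cannot be detected at all, or that an asymptomatic laboratory change can never reach the results. The documents support neither reading: the route exists, although it depends on individual judgement and does not replace a summary by arm.

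A reader might also infer that the trial must test the HPA axis, because Section 22.a says "Systemic absorption of topical corticosteroids has produced reversible suppression of the HPA axis" and the list in Section 15 ("comprehensive blood count (CBC), metabolic panel (CMP), blood HIV/Hepatitis B/Hepatitis C testing, urinalysis, urine pregnancy, urine drug screen, breath alcohol tests") contains no such test. That does not follow. The sentence is a general one about topical corticosteroids, calls the effect reversible, and sets no monitoring aim. Visit 4 falls on Day 15±2, so a sample at that visit could be taken up to three days after a last dose on Day 14. Whether a 14-day pilot should include such testing is for the sponsor.

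Two further limits are fair. The only chemistry analytes the documents name are ALT, AST and total bilirubin, so claims about other analytes cannot be checked. No SAP text beyond Section 23 was available, so the statement that no laboratory summary is planned applies to the supplied text.

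**Conclusion.** The point holds in this form. Post-dose vital signs are not scheduled although Section 24.b.v presupposes them. The collected CMP and CBC values have no planned summary, except where an investigator records an abnormality as an adverse event. The conclusion on objective b therefore rests on reported adverse events.

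In size: no scheduled post-dose vital-sign values, and about 300 CMP and 200 CBC results without a planned comparison if all 100 subjects complete. A summary by arm would estimate a difference in mean change to within about 0.40 SD, assuming 50 evaluable subjects per arm, and less precisely with loss. The documents give no expected effect on any of these measures, so the size of a missed effect cannot be stated.

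This is an inexpensive improvement to the safety evidence. It does not touch the efficacy comparison. The vital signs matter more, because data not collected cannot be recovered; the laboratory tables could still be produced later from data in hand.

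**What to change.** 1. Reconcile Section 24.b.v with Sections 10, 22.b and 28 by repeating the seated vital signs at Visit 4 and at the early-discontinuation visit. In Section 23.b, tabulate change from Visit 1 by arm, with 95% confidence intervals for the difference. Cost: about five minutes per subject at an existing visit. Limit: because of the Visit 4 window, some readings will be taken shortly after treatment has ended. Routine vital signs at Visit 5 for completers are not needed for this purpose, since they would come about two weeks after treatment.

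2. In Section 23.b, add change from Visit 1 and shift tables by arm for the CMP and CBC already collected, with the number of subjects reaching each liver threshold in Section 22.e. Give the number with a value at each visit, because early leavers may have no post-dose panel. Cost: a few standard tables and no new procedure.

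Neither change alters dosing, withdrawal or any other clinical rule.

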- 7. When the Subject has completed all screening procedures, compliance with the inclusion and exclusion criteria will be reviewed. (See Sections 12 & 13 Inclusion & Exclusion Criteria) After the inclusion and exclusion criteria have been confirmed, the Subject will be randomized to a treatment group. The Subject will be assigned a randomization number (See Section 11. Randomization).
- 8. The following will be dispensed during Visit 2:
 - The Investigational Product (28 suppositories)
 - A diary card to record IP Use, Adverse Events and Concomitant Medications along with instructions on how to complete.
 - Backup diary cards to record missed ePRO questionnaires (as needed)
- 9. Randomized Subjects will be instructed on the correct method for the application of the Investigational Product. The first application of the Investigational Product will be performed by the Subject at home. The study restrictions will also be reviewed with the Subject and an instruction sheet will be issued to the Subject. (See Section 14. Treatments)
- 10. Randomized Subjects will be instructed how and when to complete the diary for Study Medication use. They will be told that they are to document all treatments administered, including the date and all treatments missed. In addition, Subjects will be reminded to document all AEs. Subjects will also be instructed to call the study site if they experience any severe intolerability to Investigational Product.
- 11. PROMIS Global Health questionnaire will be performed.
- 12. Study instructions will be reviewed with the Subject, including the procedure for application of the Investigational Product. (See Section 14. Treatments)
- 13. Visit 3 (Day 8 ± 1 days from the date of Visit 2) will be scheduled and the Subject will be instructed to bring the Subject's diary and backup ePRO diary (if applicable) with him or her to this visit.

3. Visit 3: Interim Visit (Day 8±1)

The following procedures will be performed at Visit 3:

- 1. Appropriate study personnel will review the use of IHSSA with the Subject. (See Appendix 1)
- 2. The use of concomitant medications since the previous study visit will be documented and assessed for each Subject. (See Section 22. Subject Safety)
- 3. A urine pregnancy test will be conducted for all female Subjects of childbearing potential.
- 4. Blood sample will be collected from the Subject for clinical laboratory tests: comprehensive metabolic panel (CMP).

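### Do the conflicting placement of Day 15 (Sections 5 and 23) and the unpaired one-week PGIS recall undermine the IHSSA analysis?

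*Combined protocol and SAP*

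**What the plan says.** Section 5 (Study Design) gives "Treatment Period (2 weeks/ Days 1-14") and "Follow-up Period (2 weeks/ Days 15-29"). Section 23 (Statistical Methods, Endpoints) says "IHSSA scores from Days 1-15 (treatment period) and 16-29 (follow-up period) will be compared to responses from Days -14 to -1 (baseline period"), followed by 95% confidence intervals for the difference between arms in change from baseline. The end-of-treatment visit in Section 9 is "Visit 4 (Day 15±2, End of Treatment").

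Section 14 has two suppositories a day for 14 days. Section 28 dispenses 28 at Visit 2, adds that "The first application of the Investigational Product will be performed by the Subject at home", and has unused product returned at Visit 4.

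On the anchors, Section 21.d says "The 8-item PGIS asks patients to rate the severity of their hemorrhoid-related signs and symptoms over the past week", that "The 9-item PGIC asks patients to rate the direction and magnitude of the change in their signs and symptoms since starting the study medication", and that "The PGIS and PGIC are included in the study to help establish the threshold for clinically relevant change on the IHSSA". PGIS is taken at Visits 2 and 4, and PGIC at Visit 4. The IHSSA is completed daily for the whole study (Section 5; Section 10, footnote 7). Section 21.b and Appendix 1, which describe the IHSSA, are partly withheld from the public text.

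**The concern.** Two current sections place Day 15 in different periods, and both use calendar days although the first dose is taken at home at an unstated hour. If Visit 4 falls on Day 13 and the remaining product is handed back, Days 14 and 15 still count as treatment under Section 23.

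Section 23 also does not say whether the daily scores are averaged, taken at their worst, or taken at the last value. PGIS looks back seven days, while Section 23's baseline and treatment windows are 14 and 15 days long.

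The pilot is meant to inform endpoint selection for later studies and to help set a threshold for meaningful IHSSA change. If that threshold were derived from a 15-day mean and then applied to a last-week endpoint, it could be too small when benefit builds gradually.

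**Working it through.** **Period lengths.** Section 5: Days 1-14 = 14 days and Days 15-29 = 15 days. Section 23: Days 1-15 = 15 days and Days 16-29 = 14 days. Only Day 15 moves.

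**Supply against the boundaries.** The plan's figure reproduces: 2 per day × 14 days = 28. A Day 1 morning start uses the last dose on the evening of Day 14, which fits Section 5. A Day 1 evening start uses it on the morning of Day 15, which fits Section 23. Each boundary fits one start time.

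**What Day 15 is worth.** If the effect is constant through Day 14 and absent on Day 15, the Days 1-15 mean is 14/15 = 0.933 of the Days 1-14 mean, a loss of 6.7%. Now suppose the effect rises linearly, (t−1)/(F−1) on day t up to full on Day F, and holds on Day 15. The largest change from adding Day 15 is at F = 14: Days 1-14 mean = 7/14 = 0.500, Days 1-15 mean = 8/15 = 0.533, a gain of 6.7%. For F = 1, 2, 4 and 7 the gain is 0, 0.5, 1.1 and 2.2%.

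**Early Visit 4.** With Visit 4 on Day 13, the days after product return are 2/15 = 13% of Section 23's treatment period and 1/14 = 7% of Section 5's. This applies only to subjects seen that early, and the rule is the same in both arms.

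**PGIS recall.** The week before Visit 2 covers 7/14 = 50% of the baseline window. The week before Visit 4 on Day 15 is Days 8-14, or 7/15 = 47% of the treatment window. Across Visit 4 on Days 13 to 17 it runs from Days 6-12 to Days 10-16. On Day 17 one recall day is follow-up under Section 23 and two are under Section 5.

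**Size of the feared dilution.** The same linear onset is assumed, with Day 15 keeping the Day 14 effect. The documents give no onset time.

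| Full effect on Day | Mean, Days 1-15 | Mean, Days 8-14 | Ratio |
|---|---|---|---|
| 1 | 1.000 | 1.000 | 1.00 |
| 2 | 0.933 | 1.000 | 0.93 |
| 4 | 0.867 | 1.000 | 0.87 |
| 7 | 0.767 | 1.000 | 0.77 |
| 14 | 0.533 | 0.769 | 0.69 |

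If Day 15 lost the whole effect, the last row would be (7/15)/0.769 = 0.61.

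**Would a last-week contrast be more sensitive?** All variance inputs here are assumed: day-to-day autocorrelation 0.3-0.6, daily SD 0.5-0.8, between-subject SD of change 0.5. The signal-to-noise ratio of 7/7 days over 14/15 days is 0.82-0.92 for F = 1, 0.88-0.98 for F = 2, 0.95-1.06 for F = 4, 1.07-1.19 for F = 7 and 1.19-1.32 for F = 14. It runs from a loss to a gain, depending on an onset time nobody yet knows.

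**The case for a change.** The strongest case for acting is that the threshold and the endpoint definition are main products of this pilot, both depend on the window, and the wording would cost almost nothing because dose dates and daily scores are already collected. A subject who stops at a Day 13 visit could have taken about 23 to 25 of 28 doses (82-89%). That meets the 80% rule in Section 20, so off-drug days can enter the per-protocol data.

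The facts in this stand; the consequence does not follow. Section 5 describes conduct, and Section 23 states the analysis days. Its boundary agrees with the nominal end-of-treatment visit and with its own anoscopy comparison at Day 15. Fixed study days treat both arms alike. First-dose-to-last-dose windows would depend on adherence and stopping after randomization, which may differ by arm. Seven days ending on the last dose would reach into pre-dose days for anyone stopping before Day 7.

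Nothing readable says the 14- and 15-day windows will be used with the PGIS; they serve the treatment contrast. An anchor-based threshold normally rests on total within-patient change, including placebo response and natural course, so the ratios in the table are not a measure of threshold bias unless total change follows the same curve. PGIC asks about change since starting medication and does not share the one-week mismatch.

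**Conclusion.** No change to the plan follows. The Day 15 discrepancy is a clerical slip worth at most about 7% of a treatment-period mean, assuming either that the effect holds on Day 15 or that a constant effect vanishes that day. Section 23 settles it for the analysis.

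The unnamed summary is a gap that analysts fill sensibly. A change from baseline between multi-day periods points to a per-subject period summary, and Section 12 already averages itch over two weeks and expresses bleeding as a share of bowel-movement days. A rule may also stand in the withheld parts of Section 21.b or Appendix 1.

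The PGIS pairing is the more substantial omission, but an analyst would normally match a seven-day recall to the seven diary days before each visit. Daily entries continue to Visit 5, so the plan provides those data for any permitted Visit 4 date. The harm needs three things together: a 15-day mean used as the anchored score, a slow onset, and transfer of the threshold to a weekly endpoint. The plan states none of them. Dose-date windows and an added last-week contrast are trade-offs, with assumed signal-to-noise from 0.82 to 1.32, and not corrections.
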